6.7.2.2.9 Reports of Overdose

The doses of 0.3 mg/kg and 0.5 mg/kg are expected to be well-tolerated. The half-life of PZ-128 ranged from 1.3 to 1.8 hours in volunteers with CAD risk factors, so the blood levels of PZ-128 will be substantially lower in 8 hours (i.e., 3 to 4 half-lives).

Overdose is defined as any single dose above the maximum dose allowed by the clinical protocol.

The effects of overdose of PZ-128 in humans are not known. Potential adverse effects include bleeding, anaphylaxis and thrombophlebitis/injection site irritation based upon the experience in the previous phase 1 study which involved the administration of PZ-128 at dose levels up to and including 2 mg/kg. Although there are no known antidotes to overdose, in case of overdose, the subject should be closely monitored, and supportive treatment should be administered to treat the presenting clinical manifestations. Bleeding events should be treated according to standard clinical practice, depending upon the location and severity of the bleed. In severe cases, the administration of platelets may be considered, as it may counteract the pharmacologic effect of PZ-128.

Information on overdoses in clinical subjects will be collected by the sponsor. Should a subject experience an overdose during the course of the study (whether symptomatic or not), the investigator or qualified designee must contact the sponsor within 5 working days of the investigator or qualified designee first becoming aware of the overdose. Follow-up information on the outcome of the overdose should be forwarded to the sponsor.

Any event associated with, or observed in conjunction with, a product overdose (whether accidental or intentional) or a product abuse and/or withdrawal is considered an AE should be reported as such (**Section 6.7.2.2**). If a serious adverse event occurs in conjunction with the overdose, then the reporting time frame for an SAE (24 hours) must be met. The sponsor's representative will provide instructions on how to collect this information.

6.7.2.2.10 Protocol-Specific Exceptions to SAE Reporting to Sponsor

Suspected clinical endpoint events that are also serious adverse events are to be recorded in the subject's eCRF (bleeding or clinical efficacy endpoint modules), but will **not** be reported in an expedited manner to the sponsor's SAE contact as serious adverse events. The suspected endpoint events recorded in the eCRF will be monitored in aggregate by the DSMB at appropriate intervals in order to detect any potential imbalance between the study arms which would suggest that the events are occurring more frequently or at higher severity in the study drug treatment group than the control group.

Specifically, the following events will **not** be reported in an expedited manner to the sponsor's SAE contact:

- activity/efficacy endpoints- MACE- any of cardiovascular death, non-fatal MI, non-fatal stroke, recurrent ischemia requiring hospitalization, or urgent coronary revascularization with PCI or CABG; and stent thrombosis
- safety endpoints- any bleeding that does **not** result in death, regardless of severity

Note that death unrelated to cardiovascular disease and death attributable to bleeding **will** be reported in an expedited manner to the sponsor's SAE contact.

6.7.2.2.11 Reporting of Investigational Medicinal Product Quality Complaints

Any defect or possible defect in an investigational drug product (defined as a pharmaceutical form of an active substance or placebo being tested or used as a reference in a clinical trial) must be reported by the investigator or qualified designee to the sponsor **within 24 hours** of first becoming aware of the possible defect. This report to the sponsor may be made by telephone to the designated sponsor representative. The product and packaging components in question, if available must be stored in a secure area under specified storage conditions until it is determined whether the product is required to be returned for investigation of the defect. If the product complaint is associated with an SAE, the SAE must be reported separately in accordance with the protocol, and the SAE report should mention the product quality complaint.

6.7.2.3 Guidelines and Management of Special Situations

The principal investigator(s) is responsible for ensuring that procedures and expertise are available to handle medical situations including emergencies during the study. A medical emergency usually constitutes an SAE and should be reported as such (**Section 6.7.2.2**).

The Sponsor Representative/Medical Director may be contacted with any questions/concerns:

Management of Coronary Artery Bypass Surgery (CABG)

If the investigator determines that a subject requires CABG, the subject should be treated as if they had received PZ-128. Pre-surgical prep and treatment (e.g., administration of blood products) and the timing of the CABG should be based on a sufficient washout of 48 hours. The need for CABG should not require unblinding of study drug. However, in the event that it becomes medically necessary to unblind the subject, the procedures are outlined in **Section 6.4.6**.

Management of Bleeding Events

Bleeding complications should be managed according to usual clinical practice and may include the administration of blood products. While high levels of platelet inhibition are achieved, especially after the IV infusion of PZ-128, the effects of the drug are readily reversible and decline with declining blood concentrations. After a single dose with 0.3 or 0.5

mg/kg IV administration, the effects are $\geq 50\%$ recovered within about 24 hours. If a clinically significant bleeding event occurs, the following data should be obtained immediately:

- Complete blood count
- Platelet count
- Prothrombin time (PT) / INR
- Activated partial thromboplastin time (aPTT) for bleeding not associated with PCI, or peak ACT (if available) for bleeding associated with PCI

Transfusions of blood products (packed red blood cells, whole blood, platelets, fresh frozen plasma, cryoprecipitate, etc.) may be necessary for subjects with clinically significant bleeding events and these decisions are left to the discretion of the investigator. The type of blood, number of units, site of bleeding (if any), and hemoglobin value at the time of transfusion will be recorded on the case report form.

Management of Drug Allergic Reactions

Anaphylaxis precautions must be observed during PZ-128/placebo administration and for at least 1 hour following the completion of the infusion. Medical equipment and supplies needed for resuscitation (pharmacologic agents including epinephrine, anti-histamines, corticosteroids, intravenous fluids, and aerosolized bronchodilators, oxygen, devices for intubation and mechanical ventilation, tracheostomy equipment, and a defibrillator) will be readily available in the treatment area where the study drug is administered. An anesthesiologist will be available 24 hours/day at the facility for assistance with intubation, mechanical ventilation and advanced life support.

Subjects will be observed carefully for possible infusion reactions and managed appropriately if indicated. The investigator may use his/her discretion in determining the regimen to be used according to standard clinical practice and tailored to the specific clinical situation (i.e., symptoms and severity of the reaction and responsiveness). Management may include, but is not limited to the following:

- Interruption and/or discontinuation of the study drug infusion
- Antihistamine(s) (e.g., Diphenhydramine (H1), Ranitidine (H2))
- Corticosteroid (s) (e.g., Methylprednisolone)
- Brochodilator(s) (e.g., Albuterol)
- Adrenergic Agonist(s) (e.g., Epinephrine)
- Inotropic Agent(s) (e.g., Glucagon)
- Vasopressor(s) (e.g., Dopamine)
- Intubation

- IV fluids
- Oxygen

Mild to moderate symptoms include localized skin reactions (pruritus, flushing, rash) and usually can be controlled with symptom management (e.g. administration of antihistamines and/or corticosteroids) and if necessary, temporary interruption of the study drug infusion. The study drug infusion may be interrupted and/or restarted at the discretion of the investigator depending upon the type and severity of the reaction and the responsiveness to the symptom management and/or the brief (no longer than 1 hour) interruption of the infusion. Any recurrence of symptoms following an initial improvement and/or following drug re-challenge is cause for discontinuation of the study drug.

Severe symptoms, such as clinically significant hypertension or hypotension, dyspnea, bronchospasm, angioedema or generalized urticaria require immediate discontinuation of the study drug and aggressive symptom management. The criteria for the diagnosis of Anaphylaxis [48] is attached in **Appendix C**. Anaphylaxis is a medical emergency that requires prompt recognition and immediate discontinuation of the study drug and intervention/treatment. A subject who experiences anaphylaxis will not be re-challenged with the study drug.

Prompt and accurate documentation of any allergic reaction should include the following:

- Initial symptoms and course of progression
- The timing of symptom onset
- Intervention, timing and subject response
- Time of symptom resolution
- Discharge instructions (e.g., follow-up plans, prescribed medications, appropriate allergy referral, etc.) or transfer to emergency services.

The disposition and follow-up of subjects with an allergic reaction depends on the severity of the initial reaction, the response to treatment and the clinical judgment of the investigator and medical staff. Subjects with non-life-threatening symptoms should be observed for 4-6 hours after successful treatment (resolution of symptoms) if discharge is being considered. Subjects who have severe reactions/anaphylaxis with cardiovascular and/or respiratory symptoms or refractory symptoms should be admitted or treated and observed for a longer prior of time especially if the condition is not promptly resolved by therapy. Other high-risk groups include those on beta-blocker therapy who have significant reactions and those with severe late-phase or prolonged reaction. Some subjects who have problematic social situations (e.g., no phone) or live far from medical care may also require admission or prolonged observation.

Subjects experiencing any allergic reaction should be provided with education regarding risk with future exposure to agents that might initiate an allergic response and precautions at the time of discharge including instructions for seeking emergency medical care upon recurrence

of signs/symptoms.

Need for Administration of Prohibited Medications

There are no anticipated prohibitive medications in the case of a medical emergency.

6.7.3 Other Assessments

6.7.3.1 Optional Sampling for Pharmacogenomics (DNA and RNA) Analysis

Platelets, endothelium and atherosclerotic plaques express and secrete a large number of diverse pro-thrombotic and anti-thrombotic components. Prothrombotic and hemorrhagic risk may be influenced in large part by the individual's genetic make-up and accordingly, the study will explore whether DNA polymorphisms (specific DNA sequences that differ among individuals), RNA levels and microRNAs correlate with the expression of genes involved in thrombosis, inflammation, and cardiometabolic diseases and whether these genetic components correlate with PZ-128 clinical outcomes in subjects providing informed consent for the whole blood collection. A number of CAD-related genetic loci have been recently identified (n=198), but it is essentially unknown how these genetic variants are related to cardiovascular outcomes in PCI/ACS patients or whether the variants influence platelet reactivity and thrombotic risk. In particular, the newly identified PAR1 agonist, MMP-1 is significantly elevated in plasma from patients following acute myocardial infarction. A commonly occurring MMP-1 promoter polymorphism will be assessed for increased risk of myocardial infarction in subjects with high promoter activity haplotypes versus significantly decreased risk in subjects with low promoter activity haplotypes. It has also been suggested that polymorphisms in the PAR4 gene region may be associated with platelet reactivity and cardiovascular outcomes. Therefore, in an effort to determine if DNA sequence variability in PAR4 is associated with disease status and response to PZ-128, genotype for single nucleotide polymorphisms (SNPs) in PAR4 will be determined. In addition, genome-wide association studies may be performed to identify genetic factors predisposing subjects to cardiometabolic diseases which are associated with the population under study in this trial (i.e., obesity, lipid metabolism, CVD, diabetes).

In all cases of genetic analysis of DNA and gene expression analysis from the whole blood samples provided by the subjects participating in the TRIP-PCI study, strict confidentiality will be maintained. No subject names or initials will be associated with the whole blood, the derived samples (DNA, RNA, or microRNA) or the corresponding laboratory research data. More information appears in **Appendix E**.

6.7.3.2 Optional Sampling for Pharmacokinetics, Pharmacodynamics (Platelet Aggregation), Exploratory Biomarkers

Thrombin is the major protease in the coagulation cascade. Its pleiotropic activity can ultimately lead to thrombosis and tissue injury. Thrombin also has numerous direct effects on vascular cells and is the most potent activator of platelets identified to date. The purpose of this optional sampling is to gather data to further investigate the effects of PAR1 blockade on

platelet and other vascular reactivities and to continue to characterize the pharmacokinetic profile.

6.7.4 Criteria for Termination of the Trial

The DSMB (see Section 7.8 and Section 9.3.1) will retain responsibility for recommending early termination of the study to the sponsor, who will have ultimate authority/responsibility for making the decision. The criteria that the DSMB will follow to determine when to terminate the study will be described in the separate DSMB charter.

7.0 STATISTICAL AND ANALYTICAL PLAN

7.1 Study Design

This is a multi-center, prospective, randomized, double-blind, placebo-controlled, balanced-parallel-groups study to evaluate the safety of PZ-128 compared with placebo, given in addition to standard of care, in subjects undergoing non-emergent PCI or non-emergent cardiac catheterization with the intention to perform PCI.

Prior to coronary angiography, approximately 600 subjects are expected to be randomized in a 2:2:1:1 parallel, double-blind fashion to a single, 2-hour continuous intravenous infusion of either: PZ-128 0.3 mg/kg, PZ-128 0.5 mg/kg, or Placebo 0.3 mg/kg, or Placebo 0.5 mg/kg (the two placebo groups will be merged for the purposes of data analysis). The study drug infusion will be initiated within one hour prior to the start of the cardiac catheterization procedure (i.e., angiography).

The planned administration of GPI for a subject excludes that subject from participation in this study. During PCI, bail-out GPI may be used, at the investigator's discretion, in subjects with new ischemia on telemetry or ECG, worsening of angiographic coronary flow during procedure, or thrombotic complication related to stenting during PCI.

Subjects meeting the inclusion/exclusion criteria (**Section 6.3.1 and Section 6.3.2**) will follow the randomization procedures (**Section 6.4.4 and Section 6.5.2**). The randomization code and starting seed will be generated and maintained by RTI. It will not be provided to the sponsor, or sites until the database has been locked with the exceptions of parties listed in **Section 6.4.6**. The randomization will be generated using random permuted blocks, stratified by clinical site according to the urgency of the procedure at the time the operator decides to perform the cardiac catheterization (i.e., elective versus urgent).

7.2 General Aspects of Statistical Evaluation

Statistical analyses will be performed using SAS version 9.23 and, where appropriate (e.g., specific pharmacokinetic analyses) other validated software. Statistical analyses will be performed in accordance with the study protocol, and a comprehensive Statistical Analysis Plan (SAP) which will be prepared before unmasking of the data. The SAP will provide further details of the analyses and presentation of the data and will contain ground rules and data handling conventions used to perform the analyses. Both the data and the proposed methods of analyses will be reviewed continuously during the study by the study team, which includes input from statistical, clinical and data management personnel. Before database lock, a masked review will take place during which all important protocol deviations will be discussed and agreed by the team and any ambiguities in study outcomes will be adjudicated in a masked fashion by the protocol team.

The primary and secondary outcome measures will be treated as binary outcomes with any individual experiencing the event within the specified time frame after treatment classified as

positive for the outcome and other individuals classified as negative. Details of the measures will be included in the SAP.

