6.2 Participation in and Completion of the Study

The subject is considered to be enrolled in the study when the subject is successfully randomized and is assigned a study drug treatment regimen and a unique subject randomization number. A subject who receives a randomization assignment without ever receiving any amount of study drug treatment (“randomized but not treated”) is still part of the intent-to-treat (ITT) data set for efficacy endpoints and must be followed thereafter per protocol (a telephone contact may be used in lieu of the 14-day follow-up visit for those not having taken any amount of study drug). A subject who signs the informed consent to participate in the study but does not undergo a successful randomization (i.e., screen failure, withdrew consent) will not be followed beyond the point it is determined that the subject will not be randomized- no further data will be collected and the subject will not be included in safety or efficacy analyses. Information on subjects who are screened and consented for the study but fail to undergo randomization will be submitted to the sponsor as per **Section 8.2** for regulatory purposes and to establish that the study population was selected without bias.

The subject is considered to have completed the study drug treatment following cessation of the study drug infusion. Given the single-dose design of the study, once the subject has received the study drug infusion (or once a subject permanently discontinues the study drug infusion), the study drug will no longer be available to the subject.

The subject is considered to have completed the entire study when he/she has undergone the final protocol-specified contact (i.e., study telephone call at 90-days following the study drug administration). Subject participation may be terminated prior to completion for reasons described in **Section 6.3.3**. For those subjects who do not complete the entire study protocol, subject participation will be considered terminated upon the completion of the last visit or phone contact.

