- **Adverse Events Assessment (Bleeding and Non-Bleeding): Continually During Hospitalization Following Enrollment/Randomization, 14-day Visit, 30-day Phone Call**

- **Serious Adverse Events Assessment (Bleeding and Non-Bleeding): Continually During Hospitalization Following Enrollment/Randomization, 14-day Visit, 30-day Phone Call, 90-day Phone Call**
- **Suspected Clinical Efficacy Endpoint Events (MACE & Stent Thrombosis): Continually During Hospitalization Following Enrollment/Randomization, 14-day Visit, 30-day Phone Call, 90-day Phone Call**

All adverse events (AEs) (bleeding and non-bleeding) will be reported to the sponsor in the eCRF from the time of randomization through 30 days after study drug administration. Only AEs which are classified as serious adverse events (SAEs) (bleeding and non-bleeding) will be reported to the sponsor in the eCRF after 30 days up until 90 days after study drug administration. All clinical efficacy endpoint events (MACE, stent thrombosis) will be reported to the sponsor from the time of randomization through 90 days after study drug administration.

Recording of adverse events, including reports by subjects, observations by study staff, and results of laboratory tests or other procedures, is described in **Section 6.7.2.2** (Assessment and Reporting of Adverse Events). Endpoint events (and associated symptoms) are identified as part of **Section 6.7.1** (Safety/Activity/Efficacy Endpoints) and are defined specifically in **Appendix B**, and will be detailed in the separate CEC charter for purposes of adjudication.

Note that clinical efficacy endpoint events- major adverse cardiac events (**MACE**) (any of cardiovascular death, non-fatal myocardial infarction (MI), non-fatal stroke, recurrent ischemia requiring hospitalization or urgent coronary revascularization) and **definite or probable stent thrombosis**- as well as **bleeding events** (safety) are considered “Clinical Endpoint Events” and will be adjudicated periodically during the conduct of the trial. The clinical endpoint events will be monitored in aggregate by the DSMB at appropriate intervals (i.e., quarterly). As such, these clinical endpoint events will not be reported separately in an expedited manner as “serious adverse events” to the sponsor’s SAE contact (see **Section 6.7.2.2.10**- Protocol-Specific Exceptions to SAE Reporting).

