6.7.1.2 Key Secondary Endpoint (Efficacy)

The key secondary endpoint is the incidence of any component of the MACE composite through 30 days and 90 days after treatment with the study drug.

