6.7.2.2 Assessment and Reporting of Adverse Events

An adverse event (AE) is defined as any untoward medical occurrence associated with the use of a drug in humans, whether or not considered drug related. An AE can be any unfavorable and unintended sign (e.g., an abnormal laboratory finding), symptom or disease temporally associated with the use of a drug, and does not imply any judgment about causality. An adverse event can arise with any use of the drug (e.g., use in combination with another drug) and with any route of administration, formulation, or dose, including an overdose.

AEs may include the onset of new illness and the exacerbation of pre-existing medical conditions. Worsening indicates the pre-existing medical condition (e.g., diabetes, headaches) has increased in severity, frequency, and/or duration, and/or has an association with a significantly worse outcome. A pre-existing condition that has not worsened during the study, and involves an intervention such as elective cosmetic surgery or a medical procedure while on study is not considered an adverse event.

All AEs whether volunteered by the subject, discovered by study personnel during questioning, or detected through physical examination, laboratory test, or other means, and the treatment provided must be assessed by the investigator or qualified designee and recorded in the subject's source documents/medical records.

All adverse events (AEs) (bleeding and non-bleeding) will be reported to the sponsor in the eCRF from the time of randomization through 30 days after study drug administration. Only AEs which are classified as serious adverse events (SAEs) (bleeding and non-bleeding) will be reported to the sponsor in the eCRF after 30 days up until 90 days after study drug administration. All clinical efficacy endpoint events (MACE, stent thrombosis) will be reported to the sponsor from the time of randomization through 90 days after study drug administration.

The investigator must assign the following adverse event attributes:

- Adverse event diagnosis or syndrome(s), if known (if not known, signs or symptoms),
- Dates of onset and resolution,
- Severity,
- Assessment of relatedness to PZ-128 or PZ-128 placebo, and
- Action taken and/or outcome (e.g., discontinuation of study drug administration, hospitalization, etc.).

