7.3 Data Sets

Safety analysis set

Safety evaluations will include subjects who have been randomized and who have received any amount of study drug treatment. Subjects will be evaluated according to treatment actually received. The safety analysis set will be used as the primary analysis dataset for the reporting of both the primary and secondary safety analyses as described below.

Intention-to-treat analysis set

Efficacy analyses will be carried out on an intent-to-treat basis, and all evaluations will include all subjects who receive randomization assignment, irrespective of initiation of treatment, who provide at least one outcome assessment. Subjects will be analyzed according to the assigned study treatment irrespective of any treatment allocation errors.

Per-protocol analysis sets

Per-protocol analysis sets will also be defined during the masked review for total bleeding events, and key efficacy outcome measures. Subjects will be excluded from the per protocol analysis sets as a result of protocol deviations likely to influence the outcome variables (exact details of possible protocol deviations will be detailed in the SAP). Similar conclusions from both the safety analysis set and per protocol analysis set are required for a robust interpretation of the bleeding event results.

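### Read literally, the Section 7.2 scoring rule counts MACE in never-dosed subjects, and MACE before infusion, as no event in the intention-to-treat efficacy analyses

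*Combined protocol and SAP*

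**What the plan says.** Four parts of the protocol bear on how a MACE is scored.

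- **Scoring rule (7.2).** Outcomes are binary. The first half of the rule reads "with any individual experiencing the event within the specified time frame after treatment classified as"; its second half completes it with "positive for the outcome and other individuals classified as negative". There is no missing or not-applicable class. Details of the measures are left to the SAP.
- **Analysis set (7.3, 6.2).** For efficacy, "all evaluations will include all subjects who receive randomization assignment, irrespective of initiation of treatment, who provide at least one outcome assessment". Section 6.2 says that a subject randomised but never treated "is still part of the intent-to-treat (ITT) data set for efficacy endpoints and must be followed thereafter per protocol".
- **Collection (6.6.1, 6.7.2.2).** "All clinical efficacy endpoint events (MACE, stent thrombosis) will be reported to the sponsor from the time of randomization through 90 days", with the 90 days counted from dosing.
- **Endpoint window (6.7.1.2).** MACE, as the key secondary outcome, is defined by the "incidence of any component of the MACE composite through 30 days and 90 days after treatment with the study drug". Sections 6.7.1.4 and 7.6.1 tie the component and stent thrombosis windows to treatment in the same way.

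Section 7.6.2 adds Kaplan-Meier and Cox analyses without stating a time origin. No section gives a day 0 for a subject who is never infused, or says how an event before infusion is scored.

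**The concern.** The efficacy population is defined from randomisation and the scoring rule from treatment. A never-dosed subject has no time after treatment, so that subject's infarction or cardiovascular death cannot satisfy the rule and falls into the negative class. The same happens to a dosed subject whose only event precedes the infusion. In both cases the event is collected and the subject is analysed, but the event does not count.

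At stake is whether the MACE incidence is an ITT incidence. Efficacy is descriptive here, but Section 7.6.1 uses it for the risk/benefit assessment ahead of a phase 3 study, and Section 7.5.4 makes the acceptable bleeding margin depend partly on the efficacy benefit found.

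The documents also contain a route by which the event can itself cause non-dosing. Section 6.5.3 re-checks eligibility after randomisation and before infusion. Section 6.3.2 excludes STEMI during the current hospitalisation (criterion 7) and any history of stroke (criterion 9). A subject who has either event after randomisation can fail that check, go undosed, and be scored negative because of it.

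**Working it through.** The plan states no figure for this point: it gives no MACE rate, no never-dosed share and no efficacy power. The check is therefore the rule applied case by case, followed by an illustration of size.

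**Rule applied to each class of ITT subject**

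| Subject | Event collected? | Score under 7.2 |
|---|---|---|
| Dosed, event after infusion and in window | Yes | Positive |
| Dosed, only event between randomisation and infusion | Yes | Negative |
| Never dosed, MACE at any time in follow-up | Yes | Negative |
| Never dosed, no event | None to collect | Negative |

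The second and third rows are the misclassification. Both can occur. Section 6.5.2 requires randomisation early enough for pharmacy preparation, so there is always a gap before infusion, although its length is not given. Section 6.3.4 foresees subjects who leave the study before any drug.

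**Illustration: inputs**

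- 600 subjects, 400 PZ-128 and 200 placebo (7.7).
- Never-dosed share f: assumed 2-5%.
- MACE risk: assumed 6-9%. These are the composite rates on active drug and placebo in the earlier phase 2 vorapaxar trial (4.1.1), a different drug and a different composite.

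**Events lost** = 600 × f × risk

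- Low: 600 × 0.02 × 0.06 = 12 × 0.06 = 0.7
- High: 600 × 0.05 × 0.09 = 30 × 0.09 = 2.7
- Total for comparison: 600 × 0.06 = 36 to 600 × 0.09 = 54 events

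Events before infusion in dosed subjects would add to this. They cannot be sized from the documents.

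**Effect on the comparison, f = 5% in both arms**, with 9% risk without drug and 6% with PZ-128:

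- Literal rule: placebo 0.95 × 9 = 8.55%; PZ-128 0.95 × 6 = 5.70%; difference -2.85 points; ratio 5.70/8.55 = 0.67.
- All events counted: placebo 9.00%; PZ-128 5.70 + 0.05 × 9 = 6.15%; difference -2.85 points; ratio 6.15/9.00 = 0.68.

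Each absolute risk is understated by 0.45 points, and the difference does not move.

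**Unequal non-dosing, no true effect** (9% in both arms; f = 2% on PZ-128, 5% on placebo): the literal rule gives 0.98 × 9 = 8.82% against 0.95 × 9 = 8.55%, a spurious difference of 0.27 points.

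**One event that itself prevents dosing** moves the arm's risk by 1/200 = 0.5 points on placebo or 1/400 = 0.25 points on PZ-128.

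**The case against.** The strongest reply is that the other sections show what was meant. A window running through 30 and 90 days fixes an end rather than a start; events are collected from randomisation; and Section 6.2 keeps never-dosed subjects in the set specifically for efficacy endpoints, even allowing a telephone contact in place of their 14-day visit. Section 7.2 leaves detail and data-handling conventions to a SAP written before unmasking, and provides a masked review to settle ambiguous outcomes.

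This makes it likely that the events were meant to count, and the sponsor may well score them so. It does not remove the conflict. Section 7.2 already states a complete rule with a residual negative class. A SAP that follows it inherits the problem, and one that departs from it contradicts the protocol. No separate SAP text among the documents settles the matter. Counting from randomisation would also still leave never-dosed subjects without an end of window.

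The objection to the size also stands in large part. The never-dosed share is assumed. The 6-9% appears to describe that trial's PCI cohort: 24/0.06 + 13/0.09 is about 400 + 144 = 544, close to its 573 PCI subjects and far from its 1030 in total. It is a poor guide for subjects who may never have a procedure, since scheduled post-procedure troponin sampling is for PCI subjects only (6.6.3.1) and a PCI-related infarction requires PCI.

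A reader might infer that the rule dilutes the treatment effect. It does not: with equal non-dosing the difference is identical under both rules. The dilution comes from including undosed subjects, which is inherent in ITT.

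**Conclusion.** The conflict is real on the text: as written, the rule scores genuine MACE in never-dosed subjects, and MACE before infusion, as no event, in a population that is meant to include them. It should be corrected, but the consequence is limited. About 0.7-2.7 events are affected if 2-5% are never dosed and MACE is 6-9%. Absolute risks are understated in both arms, and the risk difference is unchanged if non-dosing is equal. Bias becomes possible if non-dosing differs by arm or follows from the event. Blinding makes a difference by arm less likely, and the documents give no frequency for the second route.

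Three stronger readings are not supported:

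- That the primary result is affected. Section 7.3 analyses bleeding in subjects who received some study drug, so no never-dosed subject enters.
- That the Kaplan-Meier and Cox analyses cannot be run. Their origin is an unstated detail, for dosed and undosed subjects alike, and not a demonstrated error.
- That subjects who deteriorate before dosing are known to be entered as successes. The rule permits it, but nothing shows that it will happen often, and Section 7.6.2 treats the efficacy analyses as descriptive.

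**What to change.** In Sections 7.2 and 7.6, and in the SAP before unmasking:

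1. For ITT efficacy outcomes, count events from randomisation through 30 and 90 days.
2. State the end of the window. For dosed subjects it may stay at 30 and 90 days after infusion, so that no late event now inside the window is lost. For never-dosed subjects, end it 30 and 90 days after randomisation, or after a stated nominal day 0, and time their follow-up calls from the same point.
3. Use randomisation as the Kaplan-Meier and Cox origin.
4. Keep the infusion anchor for the safety set.
5. Reconcile the Section 7.3 requirement for an outcome assessment with Section 6.2, which keeps every never-dosed subject in the set. Do not simply delete it: under Section 7.2 a subject with no outcome data would then fall into the negative class, which is the same fault. State how such subjects are handled.

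The cost is wording, because events are already collected from randomisation. The downside is that time from randomisation to the end of the window differs slightly between dosed and never-dosed subjects, by the gap before infusion.
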